8. Vital signs to be obtained within 1 hour prior to administration of BIO 300 Oral Powder and then approximately 30 minutes, 1, 2, 4, 6, 8, and 12 h following administration of BIO 300 Oral Powder
9. ECGs to be obtained within 1 h prior to BIO 300 Oral Powder administration and then approximately 1, 2, and 4 h following BIO 300 Oral Powder administration
10. Samples for PK assessment to be obtained just prior to BIO 300 Oral Powder administration and then 30 minutes, 1, 2, 4, 6, 8, and 12 h following BIO 300 Oral Powder administration. The time of the blood draw will be ± 10 minutes of the nominal time.
11. Samples for PK assessment to be obtained 24 ± 2 h following administration of BIO 300 Oral Powder
12. Samples for PK assessment to be obtained 48 ± 4 h following administration of BIO 300 Oral Powder
13. Samples for PK assessment to be obtained just prior to administration of BIO 300 Oral Powder and then 30 minutes, 1, 2, and 4 h following BIO 300 Oral Powder administration. The time of the blood draw will be ± 10 minutes of the nominal time.
14. Samples for PD assessment to be obtained -2 to 0 h before BIO 300 Oral Powder administration, and 1, 2, and 4 h following BIO 300 Oral Powder administration. The time of the blood draw will be ± 10 minutes of the nominal time.
15. Samples for PD assessment to be obtained 24 ± 2 h following administration of BIO 300 Oral Powder
16. Samples for PD assessment to be -2 to 0 h before BIO 300 Oral Powder administration, and 4, 8, and 12 h following BIO 300 Oral Powder administration. The time of the blood draw will be ± 10 minutes of the nominal time.
17. Vital signs to be obtained within 1 hour prior to administration of BIO 300 Oral Powder and then approximately 30 minutes, 1, 2, and 4 h following administration of BIO 300 Oral Powder

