8 STUDY ASSESSMENTS AND PROCEDURES

8.1 CRITERIA FOR EVALUATION

Safety:

The safety profile of BIO 300 Oral Powder will be based on the results of CBC with differential, coagulation parameters, serum chemistries, urinalysis, ECGs, and vital signs the reporting of adverse events.

Pharmacokinetics:

Blood samples will be collected at multiple timepoints after BIO 300 Oral Powder administration and processed for serum isolation. Serum concentrations of genistein aglycone will be measured from PK parameters (C_{max} , T_{max} , clearance, $AUC_{(0-24;0-48;0-INF)}$, volume of distribution, $T_{1/2}$ and drug accumulation index) which will be calculated using standard procedures and statistical analyses.

Pharmacodynamics:

Blood samples will be collected at multiple timepoints in PAXgene tubes after BIO 300 Oral Powder administration. It will be subjected to RNA sequencing to explore biomarkers which may be predictive of BIO 300 Oral Powder effectiveness.

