9.4 STATISTICAL ANALYSES

9.4.1 GENERAL APPROACH

An independent statistician using standard statistical techniques will determine statistically significant differences in the trial measurement data. Statistical significance will be set at the nominal level of $p<0.05$. Plasma concentrations (genistein aglycone; free genistein) will be measured (AUC, C_{max} , T_{max} , $T_{1/2}$) and plasma kinetic rate will be calculated using standard procedures and statistical analyses (e.g., AUC using the linear trapezoidal formula and $T_{1/2}$ using linear regression). Data will be summarized by descriptive statistics (mean/medians and standard errors/confidence intervals for continuous response variables and distribution tables or histograms for discrete response variables).

Baseline characteristics will be compared using matched-pair t-tests. The computed change from baseline will be calculated for all measured variables and expressed as the mean change from baseline

and accompanying standard deviation (SD) of the change from baseline. Repeated measures ANOVA tests will be used to compare changes in scores for each variable between each treatment group. Matched pair t-tests will be used to compare the change scores within each treatment group. All data analyses will be conducted on the subjects who completed the study treatment periods and statistical significance will be set at $p<0.05$.

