9.2. Analysis for the Pharmacokinetic Profile

PK parameters will be estimated using nominal sampling times relative to each dose administration and nominal doses unless otherwise specified. Serum concentration values obtained at the predose time point will be used to estimate the concentration at time zero (baseline). Concentration values reported as not quantifiable (BLQ, <1.0 ng/mL) will be assigned a value of zero.

The area under the concentration vs. time curve (AUC) will be calculated using the linear trapezoidal method with linear interpolation. The AUC will not be calculated for PK profiles with less than 3 quantifiable concentrations of BIO 300 Oral Powder at separate time points. When practical, the terminal

elimination phase of each concentration versus time curve will be identified using at least three observed concentration values after Cmax, but not including Cmax. The slope of the terminal elimination phase will be determined using log linear regression on the unweighted concentration data. Parameters relying on the determination of the terminal elimination phase will not be reported if the coefficient of determination is less than 0.800, or if the extrapolation of the AUC to infinity represented more than 20% of the total area. The parameters Tmax, Cmax, AUC(0-t), AUC(0-inf) and T1/2 will be reported for each SAD cohort and for the MSD cohort on after the Day 6 dose of BIO 300 Oral Powder.

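### Straight-line AUC across the 12–24 h and 24–48 h gaps overstates AUC to 48 h by about 4–8% if half-life is 3–12 h (assumed); linear-up/log-down on the same samples usually errs less

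*Combined protocol and SAP*

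**What the plan says.** SAP 9.2 states that AUC "will be calculated using the linear trapezoidal method with linear interpolation". Protocol 9.4.1 agrees, giving "AUC using the linear trapezoidal formula" as its example of a standard procedure.

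The sampling times are in the notes to the Schedule of Activities (protocol 1.3). On the full-profile days, samples are taken before "administration and then 30 minutes, 1, 2, 4, 6, 8, and 12 h following BIO 300 Oral Powder administration". The two later draws are "Samples for PK assessment to be obtained 24 ± 2 h following administration of BIO 300 Oral Powder" and "Samples for PK assessment to be obtained 48 ± 4 h following administration of BIO 300 Oral Powder". The last two intervals are therefore 12 h and 24 h long. The four SAD cohorts and the Day 6 profile of the multiple-dose cohort share this schedule.

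Two further rules in SAP 9.2 bear on the calculation: "PK parameters will be estimated using nominal sampling times relative to each dose administration", and "Concentration values reported as not quantifiable (BLQ, <1.0 ng/mL) will be assigned a value of zero". The same section fits the terminal slope by log-linear regression. It reports AUC(0-t) and AUC(0-inf); protocol 8.1 lists AUC over 0–24 h, 0–48 h and to infinity, together with clearance and volume of distribution.

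**The concern.** If the decline is exponential, as the half-life calculation supposes, the chord across each late gap lies above the curve. The error in those gaps is always upward, so averaging over more subjects does not remove it. It grows with the length of the gap measured in half-lives, and here the two longest gaps fall in the decline.

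AUC is a primary PK output. Its absolute level enters clearance and volume (protocol 8.1), the exposure–QTcF evaluation (protocol 8.2), and the objective of identifying a putative efficacious dose from PK and PD (SAP 2.2). A rule with less error is available on the same samples.

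**Working it through.** **No figure to reproduce.** The documents state no half-life, Tmax value, expected AUC or AUC error. The sizes below rest on assumed profiles.

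**Inputs.**
- Rule: linear on every interval (SAP 9.2, protocol 9.4.1).
- Times: 0, 0.5, 1, 2, 4, 6, 8, 12, 24, 48 h, nominal (protocol 1.3, SAP 9.2).
- Assumed: noise-free one-compartment oral profile, half-life 3–12 h, Tmax 2–8 h where the model can produce both; then widened.

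**Step 1: one interval of pure exponential decline.** With k = ln 2 / half-life and gap d,

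linear / true = (kd/2) × (1 + e^(−kd)) / (1 − e^(−kd)).

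At half-life 6 h:
- 12 h gap: kd = 1.386, e^(−kd) = 0.25; 0.693 × 1.25/0.75 = 1.155, or +15.5%.
- 24 h gap: kd = 2.773, e^(−kd) = 0.0625; 1.386 × 1.0625/0.9375 = 1.571, or +57.1%.

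The 24 h gap gives +33.7% at half-life 8 h, +15.5% at 12 h and +4.0% at 24 h.

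**Step 2: a whole profile.** Take half-life 6 h and absorption half-life 1 h, so ke = 0.1155, ka = 0.6931 and C(t) = 1.2 × (e^(−ke·t) − e^(−ka·t)).
- C(12) = 0.2997, C(24) = 0.0750, C(48) = 0.00469. True AUC(0–48) = 8.616.
- 12–24 h: linear 12 × (0.2997 + 0.0750)/2 = 2.248; true 1.947; excess 0.301, or +3.5% of the total.
- 24–48 h: linear 24 × (0.0750 + 0.00469)/2 = 0.956; true 0.609; excess 0.348, or +4.0%.
- 0–12 h: −0.6%.
- Net: about +7.0%.

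The logarithmic rule on 24–48 h gives 24 × (0.0750 − 0.00469)/ln 16 = 0.609, which matches the true value. Over the whole profile, linear-up/log-down errs by −0.95%.

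**Step 3: range.** Error in AUC(0–48) at absorption half-life 1 h:

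| Half-life (h) | Linear | Linear-up/log-down |
|---|---|---|
| 2 | +3.57% | −2.40% |
| 3 | +5.67% | −1.75% |
| 4 | +6.72% | −1.37% |
| 6 | +6.96% | −0.95% |
| 8 | +6.10% | −0.73% |
| 12 | +4.13% | −0.51% |
| 16 | +2.78% | −0.41% |
| 24 | +1.38% | −0.32% |

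- Half-life 3–12 h, Tmax 2–8 h: linear +3.8% to +8.4%; linear-up/log-down −0.4% to −2.7%.
- Half-life 2–24 h, Tmax 1–8 h: linear-up/log-down was closer for AUC(0–48) in all 33 feasible pairs.
- AUC(0–24), half-life 3–12 h, Tmax 2–8 h: mixed. At half-life 3 h and Tmax 4 h, linear is +5.7% and the alternative −2.2%. At half-life 12 h and Tmax 8 h, linear is −0.3% and the alternative −1.6%.

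**Step 4: departures from the simple model.** Linear-rule error in AUC(0–48):
- Day 6 after six daily doses, half-life 3–12 h: +4.2% to +7.0%.
- Bi-exponential examples: +1.7% to +5.2%.
- Unquantifiable values set to zero, Cmax 30 ng/mL: +0.2% to +6.3%.
- Late absorption (absorption half-life up to 6 h, lag up to 2 h): +0.2% to +9.8%, against about −1% to −6% for linear-up/log-down.

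**Step 5: what it reaches.**
- Apparent clearance is dose/AUC(0-inf). In the Step 2 profile the linear AUC(0-inf) is +6.93%, so clearance is multiplied by 1/1.0693 = 0.935, about 6.5% too low. Volume derived from it shifts equally.
- Dose-to-dose ratios: equal half-lives and equal last times cancel. Half-life 4 h against 12 h leaves 1.0672/1.0413 = 1.025, about 2.5%.
- The 20% extrapolation rule: near the threshold (half-life about 20 h, Tmax 4 h) the extrapolated share is 19.5% under linear and 19.8% under the alternative.

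**The case against.** The linear trapezoid is a recognised rule, specified in advance and identical in protocol and SAP. Fitting the slope on the log scale and integrating on the linear scale are separate calculations. A reader might infer an internal contradiction, but there is none. This stands, and it limits the point to a choice of method.

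The alternative is not free of error. The amendment history says that PD draws in the multiple-dose cohort were re-timed to the Cmax observed in the SAD cohorts, and the Day 6 draws are now at 4, 8 and 12 h. Late Tmax is therefore plausible, and then linear-up/log-down errs downward by more. With half-life 3 h, absorption half-life 1 h and a 2 h lag, it gives −6.1% against +5.0% for linear. In a demanding grid of late-absorption profiles it was still closer in 1,214 of 1,368 cases (89%). Where the 48 h value is set to zero, the new rule reverts to linear on that interval and gains nothing there. One such run (half-life 4 h, Cmax 30 ng/mL) favours linear, +0.2% against −0.7%.

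Three stronger readings are tempting, and the documents do not support them:
- *The cohort 4 dose was affected.* No AUC threshold is stated for that decision, and the amendment history shows all four SAD cohorts already run by protocol version 2.0.
- *The error confounds comparisons between doses.* At half-life 8 h and Tmax 4 h, AUC(0-t) ending at 24 h carries +2.1%, and ending at 48 h, +6.3%. Nothing shows that any cohort would be unquantifiable at 48 h. Ending at 24 h would itself drop about 13% of the 0–48 h area, which neither rule repairs.
- *The 20% rule is distorted.* The shift in Step 5 could matter only to a profile already on the threshold.

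The timing objection also stands: changing the rule now alters a pre-specified primary PK calculation after SAD data exist.

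**Conclusion.** The point holds as a modest, optional-level improvement. If the profile is close to one-compartment with half-life 3–12 h and Tmax 2–8 h, the planned rule overstates AUC(0–48) by about 4–8%, almost all of it from the two late gaps. At half-life 2 h or 16–24 h the figure is about 1–4%. Linear-up/log-down on the same samples errs by about −0.4% to −2.7%, and by up to about −6% in the late-absorption runs.

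A reader might take 4–8% as a property of this trial. It is not: half-life is a study output, and every size here depends on the assumed range. Nor is the alternative unbiased; its error is usually smaller and downward. The effect is on absolute AUC, clearance, volume and the exposure–QTcF relation. It largely cancels in dose-to-dose ratios with equal half-life and last quantifiable time, and the gain for AUC(0–24) is mixed.

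**What to change.** In SAP 9.2, and in the example in protocol 9.4.1, calculate AUC by the linear-up/log-down trapezoidal rule: linear while concentrations rise or when either value is zero, logarithmic when they fall. Apply it to all cohorts, including the SAD cohorts already run, so that no comparison mixes two rules. List the linear-rule AUC beside it as a sensitivity result, which also keeps comparison with earlier work.

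The cost is a sentence in each document, a software setting and recomputation of AUCs already produced; no new samples are needed. Because the rule was pre-specified and SAD data exist, the change, its date and its reason must be recorded. Reporting both results shows that the choice was not made to suit the data.

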9.3. Analysis for Blood-Based Biomarkers

Blood-based biomarkers will be identified by extracting RNA from whole blood samples and performing transcriptome analysis to determine differential gene expression. Transcriptome analysis will be conducted by paired-end RNA sequencing. After investigating the quality of the raw sequencing data, sequence reads will be trimmed to remove possible adapter sequences and nucleotides with poor quality using Trimmomatic v.0.36. The trimmed reads will be mapped to the Homo sapiens reference genome available on ENSEMBL using the STAR aligner v.2.5.2b. The STAR aligner is a splice aligner that detects splice junctions and incorporates them to help align the entire read sequences. Binary Alignment Map (BAM) files will be generated as a result of this step. Unique gene hit counts will be calculated by using feature counts from the Subread package v.1.5.2. Only unique reads that fell within exon regions will be counted.

After extraction of gene hit counts, the gene hit counts table will be used for downstream differential expression analysis. Using DESeq2, a comparison of gene expression between the groups of samples will be performed. The Wald test will be used to generate p-values and Log2 fold changes. Genes with adjusted p-values < 0.05 and absolute log2 fold changes > 1 will be called as differentially expressed genes for each comparison. A gene ontology analysis will be performed on the statistically significant set of genes by implementing the software GeneSCF. The goa_human GO list will be used to cluster the set of genes based on their biological process and determine their statistical significance. A principal component analysis (PCA) will be performed using the "plotPCA" function within the DESeq2 R package. This plot will show the samples in a 2D plane spanned by their first two principal components. The top 500 genes, selected by highest row variance, will be used to generate the plot.

10. Safety Analyses

Summaries of safety endpoints will include data collected from the safety analysis dataset. Relevant data supporting safety analyses will be listed by subject.

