3 OBJECTIVES AND ENDPOINTS

OBJECTIVES	ENDPOINTS	JUSTIFICATION FOR ENDPOINTS
Primary Evaluate the safety and pharmacokinetics of BIO 300 Oral Powder in healthy volunteers.	
• Safety assessments including vital signs, clinical chemistries, ECG, and spontaneous reporting of adverse events.• Pharmacokinetic profile of four dose levels and profile after six days of repeated dosing	Phase 1 safety and PK analysis endpoints.

Secondary		
Characterize the expression of blood-based biomarkers	
Assessment of RNA changes related to single and multiple doses of BIO 300 Oral Powder.	Characterization of biomarkers relative to the mechanism of action that can be translated between species is a critical component of drug approval under the FDA Animal Rule.

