3.2. Secondary Endpoint

- Characterize the expression of blood-based biomarkers

4. Sample Size

- 6 subjects/cohort (3M/3F) will be recruited for the single ascending dose study, and at least 6 (3M/3F) subjects/cohort will complete all aspects of the study. 2 additional subjects (1M/1F), will be screened, consented and available as backups for each cohort.
- 10 (5M/5F) subjects will be recruited for the multiple single dose study, and at least 8 (4M/4F) subjects will complete all aspects of the study. 4 additional subjects (2M/2F) will be screened, consented and available as backups.
- In total, at least 32 healthy volunteers who will complete all aspects of the trial.

The single ascending dose study consists of 4 cohorts, each with at least 6 subjects completing all aspects of the study, split evenly to include at least 3 females and 3 males. As such, 12 females and 12 males will participate for a total of 24 subjects. The multiple single dose study will include at least 8 subjects completing all aspects of the study, split evenly to include at least 4 females and 4 males. This is a sufficient number of subjects in each study to characterize the PK and PD of BIO 300 Oral Powder and to identify dose limiting toxicities (DLTs).

5. Analysis Populations

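### The gene ontology step in SAP 9.3 uses only called genes, so it has little power for coordinated changes well below 2-fold; a set test on all Wald statistics should be added alongside it

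*Combined protocol and SAP*

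**What the plan says.** SAP 9.3 (Analysis for Blood-Based Biomarkers) sets out the sequence. At gene level, "The Wald test will be used to generate p-values and Log2 fold changes". Calling then follows: "Genes with adjusted p-values < 0.05 and absolute log2 fold changes > 1 will be called as differentially expressed genes". The process-level step comes next: "A gene ontology analysis will be performed on the statistically significant set of genes by implementing the software GeneSCF", and "The goa_human GO list will be used to cluster the set of genes based on their biological process". The only other multi-gene output is a principal component plot: "The top 500 genes, selected by highest row variance, will be used to generate the plot". That plot is descriptive and tests no process.

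SAP 9.3 does not say whether the significant set means both thresholds or adjusted p alone. Both is the natural reading, because the ontology sentence directly follows the two-threshold rule.

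Protocol 9.4.9 plans no exploratory analyses, so nothing elsewhere fills the gap. On size, SAP section 4 says "The single ascending dose study consists of 4 cohorts, each with at least 6 subjects completing all aspects of the study" and "The multiple single dose study will include at least 8 subjects completing all aspects of the study". Protocol 9.2 asserts that this is enough to characterise PD, but gives no SD, effect size or power for RNA. Protocol section 3 justifies the endpoint as follows: "Characterization of biomarkers relative to the mechanism of action that can be translated between species is a critical component of drug approval".

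**The concern.** DESeq2 yields a continuous test statistic for every tested gene. The plan reduces it to called or not called before asking any question about processes, so a gene just under either cut counts the same as a gene that did not move.

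This matters because part of the question is at process level. Protocol 2.1 describes the mechanism as estrogen receptor beta activation repressing NF-κB, which controls many immune and cell-survival genes. A modest shift of many genes in one direction is a plausible form of such a signal, and it is the form that a thresholded list handles worst. SAP 2.2 also intends to combine PK and PD profiles to identify a putative efficacious dose, so low sensitivity for some response patterns could affect how the doses compare.

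**Working it through.** **Stated figure.** 4 cohorts × 6 = 24 single-dose completers, plus 8 multiple-dose completers, gives 32, as SAP section 4 states. There is no power figure for RNA to reproduce.

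**Inputs.** From the documents: n = 6 or 8 per cohort, adjusted p < 0.05, |log2FC| > 1. Assumed, because the documents do not give them: number of genes, set size, number of sets, SD of the within-subject log2 change, inter-gene correlation ρ, true shift d, and normally distributed statistics.

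**Gene level.** For a within-subject comparison SE = SD/√n. A gene is called when its estimate exceeds max(1, z·SE). A per-gene alpha of 0.001 (z = 3.29) stands in for the adjusted p-value.
- d = 0.5 (1.41-fold), SD 0.3, n = 6: SE = 0.122. The p-value cut is at 3.29 × 0.122 = 0.40, so the p-value alone is passed with probability 0.79. The fold-change cut lies (1 − 0.5)/0.122 = 4.1 SEs above the truth, so the gene is almost never called.
- d = 0.8 (1.74-fold), SD 0.5: the chance of being called is 0.16 at n = 6, 0.13 at n = 8, 0.025 at n = 24 and about 0 at n = 100.

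Adding subjects lowers the chance, because the estimate settles on a true value below the cut. The fold-change rule, and not sample size alone, does much of the excluding.

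**Set level, main setting.** 12,000 genes; one set of m = 100; SD 0.5; n = 6; ρ = 0.05; 1,000 sets with Bonferroni (alpha 0.00005, z = 4.06).
- List test: Benjamini-Hochberg calling, then a hypergeometric test of the set. The SAP does not name the test used in GeneSCF, so the hypergeometric test is an assumption.
- Set test: mean Wald z of the set against the rest, with variance about [1 + (m − 1)ρ]/m = 5.95/100, so SE 0.244.

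The set test can be checked by hand. SE per gene = 0.5/√6 = 0.204. At d = 0.3 the mean z is 0.3/0.204 = 1.47, and 1.47/0.244 = 6.03. Power is Φ(6.03 − 4.06) = 0.98, against a simulated 97%.

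| Response in the 100-gene set | List, both thresholds | List, adjusted p only | Set test |
|---|---|---|---|
| All at 0.3 | 0% | 1% | 97% |
| All at 0.4 | <1% | 8% | 100% |
| All at 0.5 | 3-6% | 49% | 100% |
| All at 0.6 | 42-45% | 92-95% | 100% |
| 10 genes at 1.0 | 91-92% | >99% | 1-2% |
| 20 genes at 1.0 | about 100% | 100% | 46-52% |
| 30 up, 30 down, by 0.8 | about 100% | 100% | 0% |

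Ranges span repeated simulations. With no shift, every column was 0%.

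**Sensitivity.** A second model used 15,000 genes, a set of 50, 5,000 sets, ρ = 0.1, SD 0.3-0.7 and n = 6-8.
- d = 0.5: list (both thresholds) 0-3%; set test 78-100% within subject and 20-100% between two cohorts.
- d = 0.8: list 3-89%; set test 90-100%.
- ρ = 0.2, d = 0.5, SD 0.5-0.7: the set test falls to 26-95% within subject and 4-46% between cohorts.
- Type I error of the set test was 4.5% at a nominal 5%, with ρ treated as known.

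**The case against.** The strongest reply is that the planned analysis suits a biomarker search. Protocol 9.1 frames the secondary hypothesis as a change in one or more genes, and Protocol 9.4.3 looks for differentially expressed genes. A marker that carries over between species may well be a single, clearly changed gene, for which a fold-change threshold is defensible. Ontology analysis then describes the called genes. All of this stands, and so does the reply that list-based ontology after DESeq2 is a workable method.

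The reply also defeats any proposal to replace the list test. The uniform same-direction shift is the case most favourable to a directional set test. For sparse strong responses, or processes whose genes move both ways, the list test wins clearly (lower rows of the table). A uniform shift of 0.2 gives 0% for the list and about 50% for the set test, but that must not be read as describing a set in which only some genes move. With the same average of 0.2 made up of 20 genes at 1.0, the list test finds the set almost every time.

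Three stronger readings are tempting, and the documents support none of them.
- That 6 to 8 subjects cannot show such changes gene by gene. The documents give no RNA SD, and at SD 0.3 the p-value alone is passed 79-92% of the time at d = 0.5.
- That moderate changes are invisible. A broad shift of 0.6 reaches the list in 42-45% of runs, and more often if adjusted p alone defines the list.
- That an empty ontology table would count as evidence of an inactive dose. No section says so.

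What the reply does not answer is that nothing in the plan is sensitive to broad shifts well below 2-fold, although the statistics needed to look for them are already produced.

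**Conclusion.** The concern holds as a gap in sensitivity. On the two-threshold reading, the ontology analysis has little power for coordinated same-direction changes well below 2-fold: about 0-6% at log2 shifts of 0.3 to 0.5, where a correlation-adjusted set test has 97-100% in the main setting. The cause is the fold-change cut together with small n. If adjusted p alone defines the list, the loss is smaller but still large below a shift of about 0.5.

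The sizes are illustrative. They rest on assumed SD, correlation, set size and response shape, and on normal statistics. The gain shrinks at higher correlation and in between-cohort comparisons, and becomes a loss for sparse or two-way responses. The two tests are therefore complementary. The endpoint is secondary, and nothing in the documents is contradictory or invalid on this point.

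**What to change.** In SAP 9.3:
1. Prespecify a correlation-adjusted set test on the Wald statistics of all tested genes (for example CAMERA), over the same goa_human sets, for each planned comparison.
2. Keep the GeneSCF list analysis alongside it, with neither replacing the other.
3. Apply false discovery rate control that covers both analyses.
4. State whether the significant set passed to GeneSCF means both thresholds or adjusted p alone.

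The cost is SAP wording and one more script on output that the plan already produces. No new samples or visits are needed. The protocol synopsis holds PD samples until all phase 1 studies are complete before sequencing, so the method can be fixed before any data are seen; adding it after an empty list would be post hoc. The downside is a second set of process results and a slightly stricter multiplicity adjustment.
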